14.4 Laboratory Test Abnormalities

Any clinically significant laboratory test result that meets the criteria for an AE (see [Section 14.1](#)) or SAE (see [Section 14.3](#)) must be recorded on the AE eCRF, in addition to being recorded on the appropriate laboratory test results eCRF and the original laboratory report, as applicable. In these cases, P will typically require additional information about the clinically significant abnormality, including information regarding relationship to test article, any action taken, and outcome. Clinically significantly laboratory abnormalities that qualify as SAEs must be reported to the Sponsor and IRB as per [Section 14.3](#).

14.5 Pregnancy

WOCBP (see [Schedule of Events](#) for definition of WOCBP) must have a UPT prior to study enrollment. Prior to study enrollment, WOCBP must be advised of the importance of avoiding pregnancy during the study and the potential risk factors for an unintentional pregnancy. The subject must sign an informed consent form documenting this discussion.

WOCBP should be instructed to contact the investigator immediately if they suspect they might be pregnant (e.g., missed or late menstrual period). If a subject or investigator suspects that a subject may be pregnant at any time during the study, the test article must be withheld until the results of laboratory pregnancy testing are available. If pregnancy is confirmed, the subject must not receive or apply further test article and must be discontinued from the study unless the Medical Monitor elects to retain the subject to follow the subject for safety only for all or part of the remaining study period.

If following initiation of study treatment, it is subsequently discovered that a subject was pregnant or may have been pregnant at the time of test article exposure, the investigator must immediately notify the Medical Monitor of this event and record the pregnancy on the appropriate pregnancy surveillance form. The form will be sent to [PP](#). The investigator must notify the IRB of any pregnancy associated with the study treatment and keep careful source documentation of the event.

Protocol-required procedures for those subjects that are discontinued from the study must be performed on the subject unless contraindicated by pregnancy (e.g., x-ray studies). Other appropriate pregnancy follow-up procedures should be considered if indicated, including counseling of the subject by the investigator and her managing physician or health care provider (e.g., obstetrician). In addition, the investigator must report to [PP](#) on the appropriate pregnancy surveillance form(s), any follow-up information regarding the course of the pregnancy, including perinatal and neonatal outcome. Although pregnancy itself is not an AE, any complications during pregnancy should be recorded as AEs or SAEs (if they fulfill the SAE criteria). Offspring should be followed for a minimum of eight weeks. Any congenital anomaly/birth defect in a child born to a subject exposed to the test article(s) should be recorded as a SAE with details documented in the pregnancy surveillance form. Abortion, whether accidental, therapeutic, or spontaneous should be reported as an SAE.

Male subjects who are not surgically sterile (e.g., vasectomy performed at least six months prior to study entry) and are sexually active with a female partner who is of childbearing

potential¹¹ must agree to use an effective form of birth control¹² for the duration of the study. Prior to study enrollment, subjects must be advised of the importance of avoiding pregnancy during study participation and the potential risk factors for an unintentional pregnancy. The subject must sign an informed consent form documenting this discussion.

During the study, all subjects should be instructed to contact the investigator immediately if they suspect that their sexual partner might be pregnant (e.g., female sexual partner has missed or late menstrual period).

If the subject suspects that their sexual partner may be pregnant at any time during the study, or if following initiation of study treatment, it is subsequently discovered that a trial subject's sexual partner was pregnant or may have been pregnant at the time of test article exposure, the investigator must immediately notify the IRB of any pregnancy associated with the study treatment and keep careful source documentation of the event, including abortion (accidental, therapeutic, or spontaneous) and birth of offspring. Offspring should be followed for a minimum of eight weeks and any congenital anomaly/birth defect in a child born to a subject's sexual partner that was exposed to the test article(s) should be documented.

15. BLINDING/UNBLINDING

Blinding is important for the integrity of this clinical study. However, the blind may be broken in the event of a medical emergency in a subject, in which knowledge of the test article identity is critical to the subject's management. Before breaking the blind for a subject, the investigator should determine that the information is necessary (i.e., that it will alter the subject's immediate management). In many cases, particularly when the emergency is clearly not test article related, the problem may be effectively managed by assuming that the subject is receiving active product without the need for unblinding. The need to break the blind should first be discussed with the responsible Medical Monitor and the best method to do this will be determined.

¹¹ WOCBP include any female who has experienced menarche or is 10 years of age or older and who has not undergone successful surgical sterilization (hysterectomy, bilateral tubal ligation [at least six months prior to initiation of treatment], or bilateral oophorectomy) or is not postmenopausal (defined as amenorrhea >12 consecutive months in women 50 years of age and older).

¹² Effective forms of birth control include: 1) male condom with spermicide; or 2) use by the female sexual partner of a) hormonal contraceptives [e.g., oral stabilized for at least one full cycle (e.g., four to eight weeks); transdermal, injectable (e.g., Depo-Provera), implantable, or vaginal ring (e.g., NuvaRing) stabilized for at least one week prior to study entry or initiation of sexual relations], b) an IUD for at least one week prior to test article application, or c) a barrier method [e.g., female condom, contraceptive sponge, diaphragm, or cervical cap] with spermicide. Abstinence is also an acceptable method of birth control for subjects who are not sexually active. Subjects who become sexually active or begin to have relations with a female partner who is of childbearing potential during the study must agree to use an effective form of birth control for the duration of the study and for 90 days after completion of treatment (if needed).

The test article vials will be color coded with white or yellow labels to maintain the blind. Target Plaque A (LEFT) will receive the test article in the vial with a white label. Target Plaque B (RIGHT) will receive the test article in the vial with a yellow label.

16. CLINICAL SUPPLIES

16.1 Test Article Information

Test articles will be packaged and labeled by PPD Corporation. Detailed information on the packaging/labeling, blinding/unblinding, storage and preparation, dispensing, accountability, etc. is included in CCI [REDACTED]

16.2 Supplies Provided by Therapeutics, Inc.

- eCRFs
- Source document draft templates
- Site regulatory binder
- UPT kits
- Triamcinolone cream, 0.1% to treat psoriasis plaques on the CCI [REDACTED] (NOTE: subject will be responsible for purchasing OTC hydrocortisone cream or ointment as/if needed and used under the direction of the investigator)
- Bland emollient to treat areas that are not designated Target Plaques
- CCI [REDACTED] syringes for test article application
- CCI [REDACTED]
- CCI [REDACTED]
- CCI [REDACTED] digital camera

16.3 Supplies Provided by Investigator

- Personal computer to store and view study images
- Urine collection containers for UPTs, if not provided by the Clinical Lab
- Centrifuge to process blood samples

16.4 Supplies Provided by the Clinical Laboratory

- Supplies to collect and transport urine and blood samples to the clinical laboratory

16.5 Supplies Provided by PPD

- Samples for demonstration to subjects of test article application

17. STATISTICAL CONSIDERATIONS

17.1 Sample Size

This is a pilot, proof of concept study, therefore, no formal sample size calculations were performed for this study.

17.2 Analysis Populations

17.2.1 *Safety Population*

The Safety population will include all randomized subjects who received and applied test article.

17.2.2 *Intent-to-Treat Population*

The intent-to-treat (ITT) population will include all randomized subjects who were dispensed the test article.

17.2.3 *Per-Protocol Population*

The per-protocol (PP) population will include a subset of the ITT population who completed the study without significant protocol deviations (as will be determined prior to unblinding the randomization).

17.3 Endpoints

17.3.1 *Efficacy Endpoints*

For each endpoint listed below the change from Baseline will be calculated for each treatment at Visits 3, 4, 5, 6, 7, 8, and 9 and summarized. The within subject difference in the change from Baseline scores between DUR-928 and VEH will also be calculated at each visit and summarized as the proportion of subjects in which DUR-928 is better than VEH, DUR-928 is the same as VEH, and DUR-928 is worse than VEH.

1. IGA Score.
2. Clinical Signs of Psoriasis (plaque elevation, scaling, and erythema).
3. LPSI (as a sum of all three parameters including plaque elevation, scaling, and erythema).
4. Target Plaque Area (will only be calculated at Visits 4, 6, and 9).
5. NRS for Pruritus (will only be calculated at Visits 4, 6, and 9).

Treatment success outcomes will also be calculated and summarized as follows for each treatment at Visits 3, 4, 5, 6, 7, 8, and 9.

1. IGA – proportion of subjects with Target Plaques achieving a score of 0 or 1 representing “clear” or “almost clear” with at least 2-grade decrease in severity relative to Baseline.

2. Clinical Signs of Psoriasis – for each clinical sign (plaque elevation, scaling, erythema) the proportion of subjects with Target Plaques achieving a score of 0 or 1 representing “clear” or “almost clear” with at least 2-grade decrease in severity relative to Baseline.
3. NRS for Pruritus – proportion of subjects with Target Plaques that have a Baseline NRS score ≥ 4 and at least a 4 point decrease in NRS score relative to Baseline (will only be calculated at Visits 4, 6, and 9).
4. Target Plaque Area – proportion of subjects with Target Plaques achieving a 50% reduction in Target Plaque Area from Baseline (will only be calculated at Visits 4, 6, and 9).

Additionally, Target Plaque Comparison score results will be summarized at Visits 2, 3, 4, 5, 6, 7, 8, and 9 as the proportion of subjects with each score including, 1A = Target Plaque A is better than Target Plaque B, 0 = Target Plaque A is the same as Target Plaque B, and 1B = Target Plaque A is worse than Target Plaque B.

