	
Clinical Signs of Psoriasis and Local Psoriasis Severity Index Plaque elevation (induration), scaling, and erythema will each be scored on a 5-point scale where 0 = clear, 1 = almost clear, 2 = mild, 3 = moderate, and 4 = severe. These evaluations are an assessment of the overall or “average” degree of each of three key characteristics present within each of the two Target Plaques by the investigator or designee as the subject appears on the day of the evaluation and will be assessed individually for each Target Plaque. The LPSI is defined as the sum of scoring for plaque elevation, scaling, and erythema. LPSI will range from 0 to 12, with the highest score representing the more severe disease state.
 
Target Plaque Area The surface area of each of the two Target Plaques will be determined by tracing the border of each Target Plaque on a transparency containing a 1 cm² grid pattern and then totaling the area contained within the border. Each Target Plaque must individually be a minimum of 6 cm² and a maximum of 64 cm² in area.
 
Target Plaque Comparison Score The overall appearance of the two individual Target Plaques will be evaluated as follows: Target Plaque A is better than Target Plaque B, Target Plaque A is the same as Target Plaque B, or Target Plaque A is worse than Target Plaque B. This evaluation will not be a comparison with the condition at a previous visit, but a comparison of the two Target Plaques to determine which one appears better than the other. Note: the two plaques may have identical IGA scores but still be different based upon the comparison score.
 

Score	Comparison	

1A	Target Plaque A is better than Target Plaque B	

0	Target Plaque A is the same as Target Plaque B	

1B	Target Plaque A is worse than Target Plaque B	

 
Numeric Rating Scale for Pruritus Pruritus will be assessed using the Itch Numeric Rating Scale (I-NRS), a self-administered Patient Reported Outcome questionnaire. Subjects will indicate itch severity for each target lesion by circling the integer that best describes the worst level of itching due to psoriasis in the past 24 hours on an 11-point scale anchored at 0, representing “no itching” and 10, representing, “worst itch imaginable” The study staff should review the NRS for Pruritus with each subject and ask them to indicate the response that best describes their experience. Pruritus assessed by this evaluation should be reported as an AE only if therapy is required.
 
Digital Photography Digital photographic records of the two Target Plaques (A & B) will be generated for each plaque site at each visit (except Visit 1/Screening) before the first application of test article. To help with treatment identification, each Target Plaque site will be marked by a specific label on the photographs
	Score	Comparison	1A	Target Plaque A is better than Target Plaque B	0	Target Plaque A is the same as Target Plaque B	1B	Target Plaque A is worse than Target Plaque B

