5.1.1 Inclusion Criteria

1. Subject is a male or non-pregnant female 18 years of age or older.
2. Subject has provided written informed consent.

3. Subject has a clinical diagnosis of stable mild to moderate plaque psoriasis for at least two months.
4. Females must be post-menopausal⁶, surgically sterile⁷, or use an effective method of birth control.^{8,9} Women of childbearing potential (WOCBP) must have a negative UPT¹⁰ at Visit 2/Baseline.
5. Males (or their female partner) must agree to use an effective method of birth control throughout the study.
6. Subject has two similar contralateral Target Plaques that:
 - Are located on the upper extremities not including the palms, and
 - Must individually be a minimum of 6 cm² in area, a maximum of 64 cm² in area, and a similar size (both Target Plaques should ideally be the same size but one should not be more than about a third larger [e.g., 33%] than the smaller plaque), and
 - Must have the same IGA score of 2 or 3, and
 - Must have the same plaque elevation score of 2 or 3, and
 - Have a Target Plaque Comparison score of 0 (Target Plaque A=Target Plaque B), and
 - Are easily accessible for test article application by the subject or a reliable care provider.
7. Subject is willing and able to apply the test article(s) as directed, comply with study instructions, and commit to all follow-up visits for the duration of the study.
8. Subject, in the investigator's opinion, is in good general health and free of any disease state or physical condition that might impair evaluation of the plaque psoriasis or exposes the subject to an unacceptable risk by study participation.

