17.4.1 Efficacy Analyses

The efficacy analyses will be conducted on the ITT and PP populations.

Product Name: DUR-928 Topical Solution
Sponsor Name: Therapeutics, Inc.

Protocol: C928-015
Protocol Date: May 22, 2019, v4.0

For endpoints of change from Baseline, the comparison between DUR-928 and VEH will be conducted using a paired t-test with a significant alpha level of 0.05.

For endpoints of treatment success outcomes, the comparison between DUR-928 and VEH will be conducted using McNemar's test with a significant alpha level of 0.05.

The within subject difference in the change scores and Target Plaque Comparison score between DUR-928 and VEH will also be calculated and summarized descriptively.

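### Should change in Target Plaque Area be fixed as percent change, given that plaques range from 6 to 64 cm² and a pair may differ by a third?

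*Combined protocol and SAP*

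**What the plan says.** Section 17.3.1 gives one rule for all five continuous endpoints (IGA, clinical signs, LPSI, area, itch): "For each endpoint listed below the change from Baseline will be calculated for each treatment". It adds that "The within subject difference in the change from Baseline scores between DUR-928 and VEH will also be calculated at each visit", summarised as the share of subjects in whom DUR-928 did better, the same or worse. Area appears as item 4: "Target Plaque Area (will only be calculated at Visits 4, 6, and 9". Section 17.4.1 states that for the change endpoints "the comparison between DUR-928 and VEH will be conducted using a paired t-test with a significant alpha level of 0.05", and describes a separate descriptive summary: "The within subject difference in the change scores and Target Plaque Comparison score between DUR-928 and VEH".

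The synopsis (Study Measurements, Target Plaque Area) says that each plaque is traced "on a transparency containing a 1 cm² grid pattern and then totaling the area contained within the border". Inclusion criterion 6 in Section 5.1.1 allows 6 to 64 cm² per plaque. It asks for plaques of ideally equal size, with the limit that "one should not be more than about a third larger [e.g., 33%] than the smaller plaque". IGA and elevation scores must match within the pair, and the plaque comparison score must be 0.

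Section 17.3.1 also has a relative area outcome, the "proportion of subjects with Target Plaques achieving a 50% reduction in Target Plaque Area from Baseline", which Section 17.4.1 tests with McNemar's test.

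**The concern.** IGA and the clinical signs run from 0 to 4, LPSI from 0 to 12 and itch from 0 to 10. A plain difference from baseline means much the same thing for every subject on those scales. Area is different: a given percentage shrinkage is worth about ten times as many cm² in the largest eligible plaque as in the smallest.

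Three consequences seem to follow if the change is taken in cm². A few large plaques could decide the t-test. In an unequal pair, the better/same/worse call could reflect starting size. And because the scale is not written out, an analyst might choose it after seeing the data. With 15 to 20 subjects and a significance test at 0.05, this looks like something to settle in the plan, preferably as percent change.

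**Working it through.** The plan has no effect size, SD or power figure (Section 17.1), so there is no figure of its own to reproduce.

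**1. Arithmetic on the eligibility limits.** The size range is 64/6 = 10.7-fold, and 64/48 = 1.33, so a 64/48 cm² pair is just eligible.
- Both plaques shrink 30%: 0.30 × 64 − 0.30 × 48 = 19.2 − 14.4 = 4.8 cm² apart, but 0 points apart in percent.
- The same shrinkage in an 8/6 cm² pair: 0.30 × 8 − 0.30 × 6 = 0.6 cm².
- Direction can reverse: 0.25 × 64 = 16.0 cm² exceeds 0.30 × 48 = 14.4 cm².

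The scale does matter for individual pairs, most of all at the extreme of what is eligible.

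**2. Validity.** Because the active side is random, the 4.8 cm² in the first example is as likely to favour one treatment as the other and averages to zero. Simulated type I error with a 20% reduction on both sides is 4.0 to 5.0% on cm² and 4.8 to 5.2% on percent.

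**3. Power if shrinkage is proportional and tracing has no error.** All inputs are assumed: reductions of 35% and 20%, SD 20 points, within-subject correlation 0.5, pair ratio uniform on 1 to 1.33, two-sided test. The SD of the paired difference in percent is 20 × √(2 × (1 − 0.5)) = 20 points, so the standardised difference is 15/20 = 0.75.

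| n, baseline sizes | cm² | percent |
|---|---|---|
| 15, uniform | 65–67% | 77% |
| 15, log-uniform | 59–62% | 77% |
| 20, uniform | 79–80% | 89% |
| 20, log-uniform | 73–76% | 89% |

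The ranges cover different ways of drawing the pairs. At n = 15 the gain is about 10 to 18 points. Changing the SD to 15 or 30 points (with a 25-point effect for the latter) and the correlation to 0.3 or 0.7 brings the low end down to 3 points (96.6% against 99.6%).

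**4. Power if those assumptions change.** Tracing error is per reading; the first four rows cover n = 15 and 20.

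| Assumption | Percent minus cm² |
|---|---|
| Constant tracing SD 1 cm² | +5 to +9 points |
| Constant tracing SD 1.5 cm² | −3 to +3 |
| Constant tracing SD 2 cm² | −12 to −1 |
| Tracing SD 1.5–2 cm² at 35 cm², growing with √area | +8 to +15 |
| Additive effect, n = 15 (75–77% on cm², 58–61% on percent) | −19 to −14 |
| Additive effect, n = 20 (87–89% on cm², 72–75% on percent) | −17 to −12 |

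The sign depends on how plaques shrink and how well they are traced. The documents give neither.

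**5. Agreement between scales.** Direction differs in about 6% of subjects when pair ratios are uniform on 1 to 1.33. For 15 subjects that is 0.06 × 15 = 0.9, about one. It falls to 2% for ratios of 1 to 1.1 and to 0% for equal pairs, which the inclusion criterion describes as ideal. Significance verdicts differ in 12 to 23% of simulated trials under the assumed effect. Calling the result positive when either scale is significant gives a type I error of 6.5 to 7.1%.

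**6. How much of the analysis is affected.** Change tests: IGA 7 visits + three signs × 7 = 21 + LPSI 7 + area 3 + itch 3 = 41. Success tests: 7 + 21 + 3 + 3 = 34. That makes 75 per population and 150 over the ITT and PP populations. The area t-test is 3 × 2 = 6 of them.

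**The case for a change.** The strongest case for a change is that no sentence states the scale, that the choice alters the significance verdict in 12 to 23% of simulated trials, and that one sentence before unblinding would remove the 7% risk at almost no cost. It also seems odd for the success outcome to be relative and the continuous outcome absolute.

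The first part is correct as an observation: the scale is left to ordinary reading. That reading is not really in doubt, though. The measurement is in cm², the wording is a plain change, and the same section switches to an explicit percentage when a relative measure is meant. The 7% figure arises only if someone disregards that reading and picks a scale after unblinding. The verdict discordance shows that the two scales answer different questions; it does not show that cm² is wrong. Area cleared is a legitimate quantity, and giving more weight to large plaques is part of what it measures. Having one absolute and one relative area outcome covers both questions.

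The demand for a tolerance defining the same result is weaker still. On percent change, ±5 points would call 15% of pairs equal under the assumed effect and 20% under no effect, and ±10 points 30% and 38%. That adds an arbitrary cut-off to a table that is only descriptive.

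**Conclusion.** No change to the plan is needed. The missing unit is a detail that an analyst fills sensibly with cm², and on that reading the paired t-test is unbiased with type I error near 5%, given random assignment of treatment to side. Choosing between cm² and percent is a trade-off. At 15 subjects percent change gains about 3 to 18 points of power if shrinkage is proportional and tracing is error-free, but loses about 14 to 19 if the effect is additive. Constant tracing error of 1.5 to 2 cm² per reading removes or reverses the gain. All of these figures rest on assumed reductions, SDs, correlations and size distributions, because the documents supply none.

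What remains is that the better/same/worse call may follow starting size in about one subject of 15, and in fewer if pairs are close to equal as the criterion intends. That affects a descriptive summary of one endpoint among several, in a pilot study with no declared primary and with a relative area outcome already tested at the same visits. Showing percent change beside cm² would be a reasonable addition to the report, but nothing in the planned inference depends on it.

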4. STUDY DESIGN

This is a multicenter, randomized, double-blind, vehicle-controlled, paired-plaque, proof of concept comparison study of DUR-928 in subjects with stable mild to moderate plaque psoriasis. Eligible subjects must have two similar contralateral Target Plaques as described in [Section 5.1.1](#). Approximately 20 subjects will be enrolled at approximately three study sites to obtain about 15 evaluable subjects. The maximum proportion of subjects to be enrolled with mild plaque psoriasis is approximately 25% of the total enrolled subjects.

Each subject will receive both of the following treatments with occlusion:

1. DUR-928 Topical Solution,  and
2. Vehicle Topical Solution

Subjects will be instructed to apply the test articles once daily to the two Target Plaques at approximately the same time and follow the instructions for application and occlusion. Subjects will be allowed to use triamcinolone cream, 0.1% and/or over the counter (OTC) hydrocortisone ointment or cream 1% or 0.5% on the face/neck, trunk, buttocks, and lower extremities only no more than twice daily. Subjects will also be allowed to use a bland emollient on all areas (face/neck, trunk, buttocks, lower extremities, upper extremities) that are not designated Target Plaques no more than twice daily. There will be nine study visits. Efficacy will be measured through Investigator's Global Assessment (IGA), Clinical Signs and Symptoms of Psoriasis including Local Psoriasis Severity Index (LPSI), Target Plaque Area, and Target Plaque Comparison assessments by the investigator or designee in a blinded fashion. Efficacy will also be measured using the subject-assessed Numeric Rating Scale (NRS) for Pruritus. Safety will be measured by brief physical examinations, vital signs, clinical laboratory tests, urine pregnancy tests (UPTs, if applicable), local skin reactions (LSRs), and adverse events (AEs).

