9.3 Visit 2 (Day 1): Baseline

At Baseline, the investigator or designee will:

- Query the subject for any changes in health status since the previous visit, including concomitant medications and procedures/therapies, and document the findings.
- Reconfirm all inclusion/exclusion criteria, including identification of the Target Plaques. If the subject meets all inclusion criteria and no exclusion criteria, continue with the remaining Visit 2/Baseline procedures.
- Measure vital signs. See [Section 10.2.2](#).
- Perform a UPT for all WOCBP. The results must be negative for the subject to continue in the study.
- Perform photography of the Target Plaques.
- Perform clinical evaluations (IGA, Target Plaque Area, Clinical Signs of Psoriasis including LPSI, and Target Plaque Comparison) of Target Plaques. See [Section 10.1](#).
- Have subject perform NRS for Pruritus prior to first application of test article. See [Section 10.1.5](#).
- Assess LSRs prior to first application of test article. See [Section 10.2.3](#).
- Randomize the subject by assigning the next available (lowest) test article kit number.
- Dispense Subject Instructions (CCl [REDACTED]).
- Dispense the Subject Diary (CCl [REDACTED]).
- Document Test Article Accountability and dispense the test articles, as applicable.
- Supervise the application of the test articles and instruct the subject to record the date and time in the Subject Diary.
- Assess LSRs 15 minutes after the first application of test articles. See [Section 10.2.3](#).
- Supervise the occlusion of the Target Plaques and instruct the subject to record the time in the Subject Diary. For the first test article application only, occlusion will begin 15 minutes after test article application so that LSRs can be assessed.

- Document any AEs.
- Schedule the next visit.

9.4 Visit 3 (Day 8 ± 1): Week 1, Visit 4 (Day 15 ± 2): Week 2, and Visit 5 (Day 22 ± 2): Week 3

At this visit, the investigator or designee will:

- Query the subject for any changes in health status since the previous visit, including concomitant medications and procedures/therapies, and document the findings.
- Perform photography of the Target Plaques.
- Perform clinical evaluations (IGA, Clinical Signs of Psoriasis including LPSI, and Target Plaque Comparison) of Target Plaques. See [Section 10.1](#).
- **Visit 4 only:** Have subject perform NRS for Pruritus (see [Section 10.1.5](#)) and Target Plaque Area (see [Section 10.1](#)).

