The LPSI is defined as the sum of scoring for plaque elevation, scaling, and erythema. LPSI will range from 0 to 12, with the highest score representing the more severe disease state.

10.1.4 *Target Plaque Comparison Score*

The overall appearance of the two individual Target Plaques will be evaluated as follows: Target Plaque A is better than Target Plaque B, Target Plaque A is the same as Target Plaque B, or Target Plaque A is worse than Target Plaque B. This evaluation will not be a comparison with the condition at a previous visit, but a comparison of the two Target Plaques to determine which one appears better than the other. Note: The two plaques may have identical IGA scores but still be different based upon the comparison score.

Score	Comparison
1A	Target Plaque A is better than Target Plaque B
0	Target Plaque A is the same as Target Plaque B
1B	Target Plaque A is worse than Target Plaque B

10.1.5 *Numeric Rating Scale for Pruritus*

Pruritus will be assessed using the Itch Numeric Rating Scale (I-NRS), a self-administered Patient Reported Outcome questionnaire [10]. Subjects will indicate itch severity for each Target Plaque by circling the integer that best describes the worst level of itching due to psoriasis in the past 24 hours on an 11-point scale anchored at 0, representing “no itching” and 10, representing, “worst itch imaginable” (CC1 [REDACTED]). The study staff should review the NRS for Pruritus with each subject and ask them to indicate the response that best describes their experience. Pruritus assessed by this evaluation should be reported as an AE only if therapy is required.

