17.4 Statistical Methods

All statistical processing will be performed using SAS®. Summary tables (descriptive statistics and/or frequency tables) will be provided for Screening and/or Baseline variables, efficacy variables, and safety variables. Continuous variables will be described by descriptive statistics (n, mean, median, SD, minimum, and maximum). Frequency counts and percentage of subjects within each category will be provided for categorical data. Summaries will be provided for each treatment group.

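### Does the itch success outcome need a stated denominator and a rule for subjects with only one plaque at Baseline NRS 4 or more?

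*Combined protocol and SAP*

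**What the plan says.** Item 3 of the treatment success outcomes in section 17.3.1, repeated under Study Endpoints in the synopsis, sets the itch outcome as the "proportion of subjects with Target Plaques that have a Baseline NRS score ≥ 4 and at least a 4 point decrease in NRS score", at Visits 4, 6 and 9.

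The analysis set comes from section 17.4.1: "The efficacy analyses will be conducted on the ITT and PP populations". Section 17.2.2 defines the first of these without any itch condition: "The intent-to-treat (ITT) population will include all randomized subjects who were dispensed the test article". No NRS-evaluable subset is defined.

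For success outcomes, "the comparison between DUR-928 and VEH will be conducted using McNemar's test with a significant alpha level of 0.05". Section 17.4 adds only that "Frequency counts and percentage of subjects within each category will be provided for categorical data".

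On measurement, section 10.1.5 says "Subjects will indicate itch severity for each Target Plaque by circling the integer", on a scale from 0 to 10. Section 9.3 has NRS scored at Visit 2 before any test article is applied, and Screening (section 9.2) does not include it. Inclusion criterion 6 matches the two plaques on size, IGA, plaque elevation and comparison score, but not on itch.

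**The concern.** On a 0 to 10 scale, a fall of 4 points is possible only from a Baseline of 4 or more. As part of the success definition, the threshold is therefore redundant. It has an effect only if it restricts who is counted, yet the analysis populations contain no such restriction. Three readings are possible:

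1. All subjects in the population, with a plaque below 4 counted as not a success.
2. Only plaques at 4 or more, counted separately for each treatment.
3. Only subjects with both plaques at 4 or more.

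Reading 2 gives the treatments different denominators when eligibility is unequal, and so does not form a fully paired set. Reading 3 drops mixed pairs (one plaque at 4 or more, one below). The plan has no sentence about mixed pairs, although McNemar's test needs a result for both plaques. What seems to be at stake is the reported itch response rate, the difference between treatments, and possibly the p-value.

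**Working it through.** **Inputs.** From the documents: the 0 to 10 scale, scoring per plaque, ITT and PP populations, McNemar's test at 0.05, and about 20 subjects enrolled to give about 15 evaluable. The plan states no NRS response rate, power or sample size, so there is no figure to reproduce. It also gives no Baseline NRS distribution; everything on that point below is assumed.

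**Does the literal text give every plaque a status?** Success requires Baseline − follow-up ≥ 4. Of the 121 possible Baseline and follow-up pairs, every one that meets this has Baseline ≥ 4. A plaque below 4 with both scores observed is therefore a failure by arithmetic. A mixed pair needs no extra rule: one plaque can succeed, the other cannot, and the pair enters McNemar's table.

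**Effect on the rates.** With the same successes,

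rate among eligible plaques = rate over all subjects ÷ share of plaques with Baseline ≥ 4.

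- Share 40%: multiply by 1/0.4 = 2.5. Share 60%: by 1.67. Share 80%: by 1.25. Share 100%: no difference.
- Example with 14 of 20 plaques eligible: 6/20 = 30%, 6/14 = 43%.

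**Effect on McNemar's test.** The exact two-sided p-value depends only on the discordant counts b and c: p = min(1, 2 × P[X ≥ max(b, c)]), X ~ Binomial(b + c, 0.5).

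- Subjects with both plaques below 4 are concordant failures. Keeping or dropping them leaves p unchanged.
- Mixed pairs can be discordant. With 6:0, p = 2 × 0.5^6 = 0.031. If two of those six are mixed pairs and are dropped, 4:0 gives p = 2 × 0.5^4 = 0.125.

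**How often this matters.** Assumptions: Baseline NRS mean 4, 5 or 6, SD 2.5, within-subject correlation 0.7 or 0.9; itch reduction 60% on DUR-928 and 40% on vehicle; follow-up noise SD 1 or 1.5; scores rounded and clipped to 0–10; n = 15 or 20; 20,000 trials per scenario.

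| Quantity | All subjects | Eligible plaques |
|---|---|---|
| DUR-928 success | 26%–52% | 45%–62% |
| Vehicle success | 9%–26% | 15%–31% |

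| Exact McNemar, all pairs against both-eligible pairs | Share of trials |
|---|---|
| p-value differs at all | about 14%–61% |
| Significance at 0.05 differs | about 1%–10% |

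Power at n = 20 and noise SD 1, all pairs against both-eligible pairs, for means 4, 5 and 6:

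- correlation 0.7: 14.4% vs 8.9%, 30.7% vs 25.1%, 45.5% vs 41.9%;
- correlation 0.9: 14.4% vs 11.7%, 32.1% vs 29.6%, 48.2% vs 46.7%.

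**Error rate.** With equal 50% reductions and noise SD 1, the exact test rejects in at most 1.6% of trials under either set of pairs. The uncorrected chi-square form rejects in 2.4%–5.1%. If the smaller of the two p-values were picked, that form would reject in 3.1%–6.4%.

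**The case for a change.** The strongest case for a change is that the literal reading leaves the sponsor's own threshold clause without effect. Drafters usually mean a phrase to do something, and restricting an itch responder rate to subjects who can respond is a sensible aim. Two competent programmers could defend different tables, the rates could differ by a factor of 2 or more if few plaques itch at Baseline, and two or three sentences would settle it.

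Much of this stands. The clause is redundant on the literal reading, the documents do not say which reading was meant, and the percentages can differ widely. What does not follow is that the plan yields a wrong or unusable result. Redundant wording can be no more than careful drafting, and the item counts subjects in the same form as the other three success outcomes. Readings 2 and 3 need a subset that the plan nowhere creates. The natural remedy, testing all ITT pairs with a plaque below 4 counted as a failure, only writes down what the literal text already gives. Adding the rate among eligible plaques would be descriptive and would change no conclusion.

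The worry does not extend to scaling and erythema. Their success definition has no Baseline threshold clause, and section 10.1.1 says that IGA is not calculated from the sign scores, so the entry IGA cannot be used to work out how many plaques start too low on those signs.

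**Conclusion.** No change is needed. This is a gap in detail that analysts can fill sensibly: the denominator is the ITT or PP population, a plaque below 4 at Baseline is not a success, and all pairs enter McNemar's test. Eligibility is fixed by a score taken before the first application, and treatment is randomized between the two plaques. Mixed pairs therefore favour neither treatment on average, and the test is valid.

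The choice of reading mainly affects how the percentages look, by a factor of 1/(share of plaques at 4 or more); the documents do not give that share. The test decision differs in about 1% to 10% of trials under the assumed distributions. The difference in rates vanishes if every plaque starts at 4 or more, and the test is unaffected if no pair is mixed. The paired t-test on NRS change is not touched.

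This is one of several success outcomes in a pilot study with no formal sample size calculation. A table footnote giving the denominator and the number of plaques at 4 or more would let a reader convert one rate into the other.
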